- Supine heart rate and blood pressure will be measured and supine blood samples will be collected hourly for 4 hours after the last dose and at 8 hours after the treatment. Participants must rest supine for at least 30 minutes before each blood draw. The intravenous catheter will be removed following the 8-hour blood draw.
- At 2 hours after the 5th dose, participants will stand for 10 minutes for upright blood pressure and heart rate measurements and collection of an upright blood sample, as described above. Participants will be asked to rate the severity of common orthostatic symptoms while supine and upright.
- Urine will be collected for two 4-hour periods after the last dose followed by a 16-hour collection to finish the 24-hour cycle.
- Participants may be discharged approximately 8 hours after the last dose or, if they prefer, they may remain on the CRC for the washout day(s).
- Fixed-sodium and low monoamine and methylxanthine-free study diet will be provided after the 4-hour measurements and in the evening.

After at least a 1 day washout period, the study will be repeated with Treatment B

2. Objective and Research Question of the Main Study

Specific aims.

1. To assess normal changes in plasma and urinary levels of catecholamines following oral carbidopa administration.

We are giving 200mg of carbidopa every 6 hours for 5 doses. We expect that this treatment will decrease the formation of dopamine in the kidney so that urinary dopamine will be lowered and its precursor, urinary dopa, will be raised.

2. To assess the relationship between catecholamines and urinary sodium excretion following oral carbidopa administration.

Because of the important role of kidney dopamine in regulating urinary sodium excretion, we expect that urinary sodium excretion will be decreased as urinary dopamine falls.

3. To assess the effect of oral carbidopa administration on orthostatic changes in heart rate and blood pressure, as well as symptoms.

Because of the relationship between sodium excretion and blood pressure control, we expect that a carbidopa-mediated decrease in urinary sodium excretion may be associated with an increase in blood pressure.

4. To compare the catecholamine, diuretic, and cardiovascular responses following orally administered carbidopa in participants with POTS with those of healthy volunteers.

One of the most consistent findings in POTS is a reduction in plasma volume or blood volume.

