- Free of medications with the potential to influence BP

- Age between 18-60 years
- Male and female participants are eligible
- Able and willing to provide informed consent

4.B Exclusion Criteria

- Overt cause for postural tachycardia (such as acute dehydration)
- Significant cardiovascular, pulmonary, hepatic, or hematological disease by history or screening results
- Positive urine b-hcg pregnancy test or breastfeeding
- Evidence of cardiac structural disease (by clinical examination or prior echocardiogram)
- Hypertension defined as a BP>145/95 (off medications) or need for antihypertensive medications
- Evidence of significant conduction system delay (QRS duration >120 ms) on electrocardiogram
- Known allergy to FD&C Yellow dye 6
- Inability to give, or withdraw, informed consent
- Other factors which in the investigator's opinion would prevent the participant from completing the protocol, including poor compliance during previous autonomic studies or an unpredictable schedule
- Participants in the dose escalation phase will not be able to participate in the main study.

4.C Recruitment of Participants for Dose Escalation and Main Studies

The patients with POTS will be recruited from patients referred to the Vanderbilt University Autonomic Dysfunction Center. Control participants will be recruited from healthy volunteers known to the Autonomic Dysfunction Center, through the ResearchMatch.org database, and through emails to the Vanderbilt community.

Prospective participants come from several sources, including clinic patients, former patients and participants that read about our center on our Vanderbilt website. We do not advertise active studies on that site but we receive calls asking to be seen, evaluated or studied. If a potential participant is identified, a sample consent form is mailed to the participant for review. During a follow-up telephone or email contact, the participant decides if he/she wishes to be screened for the study. Clinic patients that are known to us may be offered the study and known to qualify in advance. Participants enrolled in the dose escalation part of the study will not be eligible to participate in the main study.

All participants with POTS will have been previously evaluated with a posture study (orthostatic vital signs with supine and upright blood work to assess hormones). Control participants will undergo a brief history and physical examination to ensure that they are healthy.

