		1100: supine BP and HR; metabolic panel; plasma catecholamines; plasma carbidopa; restart 4hr urine for catecholamines, sodium, potassium, creatinine
		1500: supine BP and HR; metabolic panel; plasma catecholamines; plasma carbidopa; start 16hr urine for catecholamines, sodium, potassium, creatinine

Table 2. Study Day Description-Dose Escalation

3

Day	Treatment	Time	Assessments for Tolerability	Obtain Consent	History & Physical	Pregnancy Test	Study Diet	Carbidopa or Placebo	Blood Draw	HR/BP	Urine
Pre-Study			X	X	X	X			X		
-3, -2						X					Start study diet
-1	0700					X					Start 24hr urine #1
1	0645					X			X	X	End & restart 24hr urine
	A 0700, 1300, 1900					X	Doses 1, 2, 3				Continue 24hr urine #2
	0900, 1500, 2100	X				X			X	X	Continue 24hr urine #2
2	0100					X	Dose 4				Continue 24hr urine #2
	0300	X				X			X	X	Continue 24hr urine #2
	0645-0700					X	Dose 5		X		End 24hr, start 4hr urine #1
	0800					X			X	X	Continue 4hr urine #1
	0900	X				X			X	X	Continue 4hr urine #1
	1000					X			X	X	Continue 4hr urine #1
	1100					X			X	X	End 4hr urine #1 & start 4hr urine #2
May be discharged	1500					X			X	X	End 4hr urine #2 & start 16hr
3(washout day)	0700					X					End 16hr urine
4	0700					X					Start 24hr urine
5	0645					X			X	X	End & restart 24hr urine
	B 0700, 1300, 1900					X	Doses 1, 2, 3				Continue 24hr urine #2
	0900, 1500, 2100	X				X			X	X	Continue 24hr urine #2
6	0100					X	Dose 4				Continue 24hr urine #2
	0300	X				X			X	X	Continue 24hr urine #2
	0645-0700					X	Dose 5		X		End 24hr, start 4hr urine #1
	0800					X			X	X	Continue 4hr urine #1
	0900	X				X			X	X	Continue 4hr urine #1
	1000					X			X	X	Continue 4hr urine #1
	1100					X			X	X	End 4hr urine #1 & start 4hr urine #2
	1500					X			X	X	End 4hr urine #2 & start 16hr
7	0700										End 16hr urine

4.G Data Elements-Main Study

- A minimum of 9 days is needed to complete the study with 2 nights on the CRC for the active compound and 2 nights for the placebo.
- Participants will be provided a 200 mEq/day sodium diet, free of methylxanthines and low in monoamines, by the kitchen of the Clinical Research Center (CRC).
- After achieving sodium balance on the study diet over 2-3 days, participants will collect urine over 24hr starting at 0700hr, for baseline assessment of sodium, potassium and catecholamines and to confirm adherence to the study diet.
- Participants will be admitted to the CRC that afternoon or evening.

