- At 2 hours after the last dose, participants will stand for 10 minutes for upright BP and HR measurements and collection of an upright blood sample, as described above. Participants will be asked to rate the severity of common orthostatic symptoms while supine and upright.
- Urine will be collected for two 4-hour periods after the last dose followed by a 16-hr collection to finish the 24-hour cycle for analysis of sodium, potassium, catecholamines, and creatinine.
- Participants may be discharged from the CRC approximately 8 hours after the last dose.
- After at least 24 hours, the protocol will be repeated with treatment B (Carbidopa 200 mg or placebo, whichever was not administered during treatment A). Depending on the interval, participants will either remain on the study diet or re-start the diet 2-3 days before admission for the 2nd phase.

4.H Schedule of Events-Main Study

Table 3 Study Schedule-Main Study

Dosing Regimen	Time of Dose	Monitoring/Labs
Predose	NA	24hr urine for catecholamines, sodium, potassium, creatinine to start 24hr prior to 1 st dose; supine and upright BP and HR; supine and upright plasma catecholamines, serum aldosterone, plasma renin activity; metabolic panel; start another urine collection over 24 hr for catecholamines, sodium, potassium, creatinine
Dose #1	0700	0900: supine BP and HR
Dose #2	1300	1500: supine BP and HR
Dose #3	1900	2100: supine BP and HR
Dose #4	0100	0300: supine BP and HR
Pre-Dose #5	0645	Supine and upright BP and HR; finish 24hr urine and start 4hr urine for catecholamines, sodium, potassium, creatinine
Dose #5	0700	0800: supine BP and HR; plasma catecholamines
		0900: supine and upright BP and HR; plasma carbidopa; Orthostatic Symptom Questionnaire; supine and upright plasma catecholamines, serum aldosterone, plasma renin activity
		1000: supine BP and HR; plasma catecholamines
		1100: supine BP and HR; metabolic panel; plasma catecholamines; plasma carbidopa; restart 4hr urine for catecholamines, sodium, potassium, creatinine
		1500: supine BP and HR; metabolic panel; plasma catecholamines; plasma carbidopa; start 16hr urine for catecholamines, sodium, potassium, creatinine

Table 4. Study Day Description-Main Study

Day	Treatment	Time	Obtain Consent	History & Physical	Pregnancy Test	Study Diet	Carbidopa or Placebo	Blood Draw	HR/BP	Urine
Pre-Study			X	X	X					
-3, -2					X					Start study diet
-1	0700				X					Start 24hr urine #1
1	0645				X			X	X	End & restart 24hr of urine collection

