Carbidopa has not been demonstrated to have any overt pharmacodynamic actions in the recommended doses. The only adverse reactions that have been observed have been with concomitant use of carbidopa with other drugs such as levodopa, and with carbidopa-levodopa combination products. Common adverse events with the carbidopa-levodopa combination include abnormal body movements and nausea. Less common adverse effects are psychotic episodes (periods of confused thinking which can include hearing voices, seeing things that are not real, believing things that are not true and/or strange behavior), depression and dementia (loss of mental ability severe enough to cause problems with normal activities of daily living). Rarely, there is an allergic reaction to the FD&C Yellow 6 dye. The dose in this study is a much higher dose than used in clinical practice, and there may be additional side effects that are not known at this time. This medication has never been used at this dose or frequency.

Study Procedures:

Venipuncture: The vein in which the needle has been inserted to draw blood may become sore and red. A temporary "black and blue mark" may develop, and rarely fainting may occur.

5.D Reporting Timeline

- Within **24 hours** (of learning of the event), investigators must report any reportable Serious Adverse Event (SAE) that:
 - Is considered life-threatening/disabling or results in death of participant-OR-
- Is Unexpected/Unanticipated
- Investigators must report all other reportable SAEs within **5 working days** (of learning of the event).
- All other (suspected) reportable AEs must be reported to the RDCRN within **20 working days** of the notification of the event or of the site becoming aware of the event.

Local institutional reporting requirements to IRBs, any Vanderbilt Institute for Clinical and Translational Research/Clinical Research Center (VICTR/CRC) oversight committee and the FDA, if appropriate, remain the responsibility of the site investigator and the Study Chair.

5.E RDCRN Adverse Event Data Management System (AEDAMS)

Upon entry of a serious adverse event by a site investigator, the DMCC created Adverse Event Data Management System (AEDAMS) will immediately notify the Study Chair and the Independent Medical Monitor. The Study Chair is responsible for notifying the appropriate NINDS staff.

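### Pregnancy is an exclusion, but the test is scheduled once, at an undated pre-study visit, and the interval to period B has no upper limit, so the plan does not verify the exclusion for each dosing period

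*Combined protocol and SAP*

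**What the plan says.** Sections 1 and 4.B exclude anyone with "Positive urine b-hcg pregnancy test or breastfeeding". Neither gives a date for the test or says how long a negative result remains valid.

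Table 2 (section 4.F) and Table 4 (section 4.H) each have a "Pregnancy Test" column, marked in the Pre-Study row beside consent and history and physical. That row has no day number, and no window ties it to Day -3 or Day 1. Section 4.C adds that some known clinic patients may be recognised as eligible ahead of time, without saying how far ahead.

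No pregnancy test is named in the admission steps of 1.B, 1.C, 4.E and 4.G, in the minimum examination list of 4.C, or in the pre-dose rows of Tables 1 and 3.

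The interval to the second period has a lower limit only. Section 1.C says: "After at least a 1 day washout period, the study will be repeated with Treatment B". Sections 4.E and 4.G say: "After at least 24 hours, the protocol will be repeated with treatment B". Both then allow for a longer gap: "Depending on the interval, participants will either remain on the study diet or re-start the diet 2-3 days before admission for the 2nd phase". Total duration is also given only as a lower bound: "A minimum of 9 days is needed to complete the study".

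On the drug, section 5.C says: "This medication has never been used at this dose or frequency". Section 8.A expects the patient group to be about 80% female; eligible ages are 18 to 60.

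**The concern.** An exclusion of this kind protects a participant only if it is known to hold when she is dosed. Here it is checked once, before either period, and neither the time from that check to the first dose nor the time to period B is capped. A woman who tests negative at the pre-study visit and becomes pregnant before period B could be dosed with every scheduled step carried out as written.

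What is at stake is participant protection. The sponsor judged the exclusion necessary, and the protocol itself describes the dosage as untried. Carbidopa is given in period A to some participants and in period B to the others, so both admissions matter, and under blinding the site cannot know which one is the active period.

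**Working it through.** **Step 1: is the test really scheduled only once?** The columns of Tables 2 and 4 are displaced in the extracted text, and the marks in later rows can appear to fall under the pregnancy-test column. They are best read as Study Diet marks:
- In the dosing rows the dose entries sit one column to the left of their header, so the mark just before them belongs to Study Diet.
- The marks appear in nearly every row, including 0300 and the washout day, which fits a diet and not a test.
- They run through Day 6 and are absent on Day 7, as the diet would be.
- If they were pregnancy tests, the Study Diet column would be empty throughout.

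That leaves one scheduled test, in the Pre-Study row.

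**Step 2: reproduce the plan's own duration.** Tables 2 and 4 use Days -3, -2, -1, 1, 2, 3, 4, 5, 6, 7, with no Day 0. That is 10 calendar days, so 0700 on Day -3 to 0700 on Day 7 is 10 - 1 = 9 intervals of 24 hours. This matches the stated 9-day minimum.

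**Step 3: age of the test on that minimum schedule.** Take the most favourable case, a test on Day -3, when the diet starts:
- First period A dose, Day 1: -3 to -2 to -1 to 1 = 3 days.
- First period B dose, Day 5: 3 + 4 = 7 days.
- Last period B dose, Day 6: 7 + 1 = 8 days.

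If the diet run-in is shortened to start on Day -2, with the test that day, the first two figures become 2 and 6 days.

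**Step 4: general case.** Let P be the days from the pre-study visit to Day -3, and G the days added to the tabulated gap between periods.
- Age at first period A dose = 3 + P.
- Age at first period B dose = 7 + P + G.

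The documents bound neither P nor G. The values below are assumptions for illustration:

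| P | G | First A dose (days) | First B dose (days) |
|---|---|---|---|
| 0 | 0 | 3 | 7 |
| 14 | 0 | 17 | 21 |
| 30 | 30 | 33 | 67 |

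**Step 5: is a longer gap only theoretical?** The tables show one washout day. The text of 4.E and 4.G, however, sets only a minimum and provides for re-starting the diet 2-3 days before the second admission, which makes sense only if some participants have gone off it. A longer gap is expressly permitted. The documents do not say how often one is expected.

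**The case against.** The strongest reply is that the tabulated schedule is short: one washout day, with period B dosing on Day 5. Nothing in the documents makes a test 3 or 7 days old invalid, so calling it out of date is a judgement. That stands for the tabulated schedule. It does not cover an earlier pre-study visit or a delayed period B, both of which the text allows, and the absence of any stated validity period is itself the gap.

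There are partial safeguards. The history in 4.C records the start date of the last menstrual period, participants are screened on the CRC (section 8), the exclusion carries no expiry wording, and the investigator may withdraw a participant (5.G). None of these requires a check before period B. The instruction to repeat the protocol with treatment B does not supply one either: in the tables the second period begins at Day 4 with a urine collection, and no Pre-Study row recurs.

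A reader might go further than the documents allow in four ways:
- *That the plan has no contraception requirement.* None appears in the supplied text, but the consent forms listed as Appendices 1a to 1d were removed, and such wording could be there. The same caution applies to a retest mentioned only in those forms; it would still leave Tables 2 and 4 to be reconciled.
- *That an undetected pregnancy would bias the sodium endpoint.* The documents say nothing about pregnancy and sodium handling, so this cannot be argued from them.
- *That about 13 of the 16 POTS completers are exposed twice* (0.8 x 16 = 12.8). This counts every woman aged 18 to 60; the number of childbearing potential is not given. In a placebo crossover each woman receives carbidopa in one period only.
- *That medications should be re-checked at the same time.* The material on the pregnancy test gives no evidence for this separate point.

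**Conclusion.** The point holds as a schedule gap. The supplied text states the exclusion but does not verify it for each dosing period. On the minimum schedule the test is at best 3 days old at the first period A dose and 7 days old at the first period B dose, taking Day -3 as the latest test day; beyond that schedule there is no upper bound.

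The conclusion rests on reading the later table marks as Study Diet and on the supplied text alone, with the consent forms unseen. It does not depend on any count of women at risk, which the documents do not provide. Nor does it mean that long gaps are planned, only that they are permitted without a repeat check.

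No sample size, power or alpha figure changes. The reason to act is participant protection at an untried dosage, set against a very small cost.

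**What to change.** Reconcile section 4.B, Tables 2 and 4, and the open-ended period B interval in 1.B, 1.C, 4.E and 4.G, so that the existing exclusion is verified for each dosing period. One way is to mark the existing urine b-hCG test at both CRC admissions (Day -1 and Day 4 in the tables), using urine already being collected. Admission is on the afternoon or evening before the 0700 first dose, so such a test would be less than a day old.

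The sponsor should state how long a negative test is valid and whether there is a maximum interval between periods; this review proposes no value for either.

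The cost is one or two extra urine tests per woman who could be pregnant, and an occasional late withdrawal.
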